10.2 Statistical Analysis

Statistical analysis will be performed using an independent samples t-test to compare change from baseline to 3 months post-intervention values from each aim (Δ HbA1c, Δ LDL-P, and Δ QOL score) between the two groups. We will also perform a series of multivariable linear regression analyses with change in primary outcomes from each aim (Δ HbA1c, Δ LDL-P, and Δ QOL score) from baseline to 12 weeks post-intervention as the dependent variable. Explanatory variables in the multivariable linear regression modeling will include mean total daily dose of insulin normalized for body mass, weight change, coefficient of variation of glucose as measured by CGM, and age.

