2.0 Rationale and Specific Aims

We hypothesize that pediatric patients with T1DM who consume a LCD will have improved HbA1c compared with T1DM patients who consume a standard-carbohydrate diet (SCD). We further hypothesize that differences in lipidemia and quality of life (QOL) between the groups will be minimal. To test our hypotheses, we will employ a pragmatic nutrition education intervention. The study will randomize adolescent patients (ages 13-21 years) to one of three groups (n = 15per group). We will instruct participants to consume a LCD (group 1) or a SCD (group 2), or provide no specific recommendations regarding diet (group 3). We will prescribe isocaloric diets for groups 1 and 2 equaling the estimated energy requirements of the Institute of Medicine⁷. Participants on the SCD intervention will consume 45-65% of total daily caloric intake from carbohydrates, 25-35% from fat and 10-30% from protein. Participants on the LCD intervention will consume 25-35% of total daily intake from carbohydrates, 45-65% from fat and 10-30% from protein. Group 3 will serve as a control that receives the same number of education sessions as groups 1 and 2 to teach general diabetes management but without specific dietary recommendations. This study design will allow for discrimination of the effect of the composition of the diet versus the effect of receiving any nutritional prescription.

Nutrition interventions are effective in producing dietary behavior change among adolescents²⁷, particularly when information and communication technologies (ICT) are incorporated²⁸. Previous brief nutrition interventions teaching LCD or low glycemic index diets in T1DM patients have resulted in appropriate dietary adherence^{29,30}. We will provide both traditional and ICT-based education and monitor dietary adherence with a smart-phone based nutritional tracking tool.

Aim 1 will provide preliminary estimates of improvement HbA1c after a nutrition intervention that teaches a LCD versus education reinforcing a SCD to families of pediatric T1DM patients. To determine the primary outcome—change in HbA1c—we will obtain HbA1c at baseline and at 12 weeks after the nutrition intervention. Additionally, we will quantify glycemic variability using continuous glucose monitoring (CGM) as a secondary outcome. Low rates of severe hypoglycemia, diabetic

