5.3 Randomization

Random permuted blocks with a fixed size of 3 will be used for randomization into treatment groups. We will stratify participants based on open vs. closed loop insulin pump use and age prior to randomization.

5.4 Participant Compensation

Research subjects will be compensated for their time and inconvenience in the study in the form money in the amounts specified below. Following study completion, participants will be mailed a check equal to the dollar amount below.

- Visit 1 (Screening visit): the initial screening visit will last approximately 2-3 hours. Subjects who complete their screening visit will be compensated \$25.
- Visit 2 (Week 1 visit): this visit will last approximately 2-3 hours. Subjects who complete this week 1 visit will be compensated \$25.
- Visit 3 (Week 12 visit): this visit will last approximately 1-2 hours. Subjects who complete this week 12 visit will be compensated \$25.
- Telephone visits (weeks 2, 4, 8): these visits will last approximately 30-60 minutes. Subjects who complete these visits will be compensated \$10 per visit.
- Participants will receive full compensation for study visits and telephone visits only if they have completed all pre-visit tasks, which will be outlined in both the consent documentation and included in the written instructions participants are given in the preceding visit.

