6.1.1.6 Randomization

We will then randomize patients to 1 of 3 groups: group 1 is low carbohydrate diet, group 2 is standard carbohydrate diet, group 3 is general diabetes education without dietary recommendation. Each group will contain 15 participants. Random permuted blocks with a fixed size of 3 will be used for randomization into treatment groups.

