10.0 Statistical Considerations

10.1 Recruitment and Sample Size Justification

We have targeted an accrual of 40 participants in this pilot study to achieve two goals. First, we require a sufficient number of participants to estimate the effect size and variance of the LCD as a means to reduce HbA1c in T1DM in a future definitive trial. We utilized the method of Whitehead et al. to estimate our pilot study's optimum accrual, which proposes stepped increases in sample size based on the anticipated standard difference, d, between interventions 41,42 . We defined the minimum important difference (MID) in Δ HbA1c between LCD and SCD interventions as 0.3% and estimated a pooled SD of 0.8% based on our literature review9. If d=MID/SDpooled=0.3%/0.8%=0.38, a sample size of 20 participants per arm will optimize future sample size calculations for the definitive study, while allowing for up to 40% dropout. Second, this sample size allows for up to 4 degrees of freedom in multivariable linear regression analysis.

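### Section 10.2 gives group 3 no role and does not say which SD goes forward; one three-group model would estimate the SD of HbA1c change more precisely from data already collected

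*Combined protocol and SAP*

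**What the plan says.** Section 10.1 gives the pilot's first purpose: "we require a sufficient number of participants to estimate the effect size and variance of the LCD as a means to reduce HbA1c". It sizes the study on an LCD versus SCD difference of 0.3% and a pooled SD of 0.8%. It arrives at 40 participants and states that "a sample size of 20 participants per arm will optimize future sample size calculations for the definitive study, while allowing for up to 40% dropout".

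The design sections describe a different layout. Section 2.0 randomises to "one of three groups (n = 15per group"), and section 6.1.1.6 repeats it: "Each group will contain 15 participants". HbA1c is drawn from every participant at visit 2 (6.1.3.2, week 0) and visit 3 (6.1.6.2, week 12). Group 3 therefore yields the same change score as the diet groups.

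Section 10.2 begins: "Statistical analysis will be performed using an independent samples t-test to compare change from baseline". The comparison is between two groups that it does not name. Aim 1 and the difference defined in 10.1 both point to LCD versus SCD. Section 10.2 then lists multivariable regressions on the same change scores. Their explanatory variables are insulin dose, weight change, the CGM coefficient of variation and age. Study group is not listed, and the participants to be included are not stated. Nothing says which SD will be carried to the definitive trial.

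**The concern.** A definitive sample size scales with the square of the SD, so imprecision in the pilot's SD passes straight into it. If the SD is taken from the LCD–SCD t-test, a third of the randomised participants contribute nothing to a quantity that the pilot exists partly to estimate. Their data cost nothing more, since they are collected anyway.

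The regressions do not fill the gap as written. Without a study-group term, their residual SD is not a within-group SD. With weight change as a covariate, which is observed after randomisation, it is also not the SD of HbA1c change that enters the standardised difference in 10.1. The t-test is thus the only specified analysis that yields an SD of the right kind.

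**Working it through.** **The plan's own figures.** 0.3/0.8 = 0.375, printed as 0.38. 2 × 20 = 40, which fits two arms only. 20 × (1 − 0.4) = 12 evaluable per arm. The figure of 20 itself cannot be reproduced, because the definitive trial's alpha and power and the step table of the cited method are not given. The point does not depend on it.

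**Inputs.** n = 15 per arm (2.0, 6.1.1.6); SD 0.8%, difference 0.3% and 40% dropout (10.1). Assumptions: complete data or equal dropout across arms (15 × 0.6 = 9); two-sided 5% and 80% or 90% power for the definitive trial.

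**Degrees of freedom.** Two groups: 2n − 2. Three groups: 3n − 3.

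**95% limits for the SD.** 0.8 × √(df/χ²), with χ² at 0.975 and 0.025.

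| n per arm | Groups | df | 95% CI for SD | Width |
|---|---|---|---|---|
| 15 | 2 | 28 | 0.635–1.082 | 0.447 |
| 15 | 3 | 42 | 0.660–1.017 | 0.357 |
| 9 | 2 | 16 | 0.596–1.218 | 0.622 |
| 9 | 3 | 24 | 0.625–1.113 | 0.488 |

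The interval is 20% narrower at 15 per arm (0.357/0.447 = 0.80) and 22% narrower at 9 per arm (0.488/0.622 = 0.78). The relative standard error of the SD, 1/√(2 df), falls from 13.4% to 10.9%, or from 17.7% to 14.4%.

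**Definitive sample size.** Using 0.8% directly gives 112 per arm at 80% power and 150 at 90%. If the trial were sized on the upper one-sided 80% limit of the SD, these are multiplied by df/χ²(0.20):
- 15 per arm: 1.297 (28 df) against 1.230 (42 df), so 145 against 138 per arm at 80% power and 194 against 184 at 90%, about 5% fewer.
- 9 per arm: 1.435 (16 df) against 1.329 (24 df), so 161 against 149 at 80% power, about 7% fewer.

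**LCD–SCD interval.** Half-width = t × 0.8 × √(2/n).
- 15 per arm: 2.048 × 0.292 = 0.598 against 2.018 × 0.292 = 0.590.
- 9 per arm: 2.120 × 0.377 = 0.799 against 2.064 × 0.377 = 0.778.

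**Cost of a wrong equal-variance assumption.** Let r be group 3's SD divided by that of the diet arms. The pooled variance is (28 + 14r²)/42 times the diet-arm variance. At r = 0.75 this is −15%, and the definitive n per arm at 80% power moves from 112 to 96. At r = 1.25 it is +19%, and n moves to 133.

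To weigh bias against precision, compare mean squared errors in units of the diet-arm variance squared, for normal data at n = 15. The two-arm estimate has 1/14 = 0.0714. The pooled estimate has ((r² − 1)/3)² + 2(2 + r⁴)/(9 × 14):
- r = 0.75: 0.0213 + 0.0368 = 0.058
- r = 1: 0 + 0.0476 = 0.048
- r = 1.15: 0.0116 + 0.0595 = 0.071
- r = 1.25: 0.0352 + 0.0705 = 0.106

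Pooling is better from about r = 0.65 to about r = 1.15, and worse outside that range.

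**The case against.** The strongest reply is that the plan never commits to the t-test SD. A reader might infer that the sponsor chose to discard group 3 when estimating the variance. The documents do not support that. Section 10.2 names neither the two groups nor the SD to be used, and its two-group wording matches the two-arm sizing in 10.1. The silence may be text that was never reconciled with a three-arm design. This part stands: what is shown is an unspecified SD and no stated role for group 3, not a deliberate choice.

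A reader might also infer that pooling restores everything that 20 per arm would have given. It does so only for the SD: 42 df against 38, or 24 against 22 after 40% dropout. The LCD–SCD half-width at 20 per arm would be 0.512, and pooling leaves it at 0.590. Nor is 28 df a clear breach of the plan. Section 10.1 tolerates 12 evaluable per arm, or 22 df, and two arms of 15 keep that up to 20% dropout (15 × 0.8 = 12).

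Finally, pooling costs no participants, but it adds an assumption. Group 3 receives no dietary prescription, and a different SD of change there is possible. For a future LCD–SCD trial the two-arm SD is directly relevant and legitimate. The pilot could hardly test the assumption: an F-test of group 3 against the diet arms at r = 0.75 or 1.25 has about 17–20% power at 15 per arm and 12% at 9. A rule to switch estimators if the SDs look different would therefore be weak as well as data-dependent. This limits the gain but does not remove it.

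**Conclusion.** The point holds as a cheap improvement. The plan should state which SD goes forward, and a three-group model would estimate it with half as many degrees of freedom again (42/28 = 24/16 = 1.5). The benefit is a CI for the SD that is about 20% narrower, and a definitive sample size about 5–7% smaller if it is based on the upper 80% limit. The documents do not state that sizing rule. The benefit for the LCD–SCD estimate itself is negligible.

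The conclusion rests on group 3 having a similar SD of change. Pooling does worse than the two-arm SD if group 3's SD exceeds about 1.15 times that of the diet arms. It also does worse if that SD is far smaller (below about 0.65 times), and the definitive trial would then be undersized.

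The degrees of freedom also assume 3 × 15 = 45, which conflicts with 40 in 10.1. Forty participants spread over three arms would give 40 − 3 = 37 against about 27 − 2 = 25. Exclusions at visit 2 (section 6.1.3), which follow randomisation at visit 1, would lower the counts further.

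**What to change.** In section 10.2:
1. Name the groups. For each outcome, fit one model of the change score with study group as a three-level factor, and take LCD minus SCD as the primary contrast.
2. State that the pooled residual SD of HbA1c change from this model, with its confidence limits, goes forward to the definitive sample size.
3. Report the three arm-specific SDs and the two-arm LCD/SCD SD beside it. Pre-specify the two-arm SD as a sensitivity value, and show the definitive sample size under both SDs. Do not add a rule that switches between them on the data.

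In section 10.1, reconcile 40 participants at 20 per arm with three groups of 15, and restate the degrees of freedom on the agreed numbers.

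The cost is a few sentences of SAP text. No participant, visit or assay is added. The price is the equal-variance assumption across three arms rather than two, which the side-by-side SDs make visible but cannot settle at this size.

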ketoacidosis and growth attenuation have been reported in pediatric T1DM patients on a VLCD¹³, therefore, we anticipate low rates of these adverse events with the LCD intervention.

Aim 2 will provide preliminary estimates of the change in the atherogenic lipoprotein profile in patients on a LCD versus SCD. The primary outcome measure will be change in total LDL-P from baseline to 12 weeks after the nutrition intervention. As secondary outcomes, we will measure the change in other contributors to atherogenic lipoprotein load, such as high-density lipoprotein particle (HDL-P) number, small LDL-P number, and LDL size.

Aim 3 will provide preliminary estimates of the change in QOL in patients on a LCD versus SCD. Participants will complete the PedsQL, a validated QOL measure in T1DM patients, and Problem Areas in Diabetes-Teen (PAID-T), a validated measure of diabetes-specific distress, at baseline (week 0) and at 12 weeks after the nutrition intervention^{31,32}. Additionally, parents of participants will complete the WHO-5 Well-Being Index, a questionnaire for assessing subjective psychological well-being³³, and Problem Areas in Diabetes-Parent Revised version (PAID-PR), a validated measure of perceived parental burden associated with caring for a child with diabetes.³⁴

We will perform an independent samples t-test to compare outcomes between groups, in addition to multilinear regression analysis to account for potentially confounding covariates, such as total daily dose of insulin, weight change, glycemic variability as measured by continuous glucose monitoring (CGM), and age.

This proposed research will be the first prospective study to determine the effect of a LCD intervention on key diabetes outcomes in a pediatric T1DM population. This study will also provide a basis of training for a new pediatric investigator in the conduct of clinical trials under the mentorship of a highly successful mentorship team including [name] and [name].

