6.1.3.2 Blood draw

Blood will be drawn from each participant and the following labs obtained:

- HbA1c
- Beta hydroxybutyrate
- NMR spectroscopy lipoprofile.

6.1.3.3 Continuous glucose monitor and insulin pump data collection

Continuous glucose monitor and insulin pump will be downloaded into a HIPAA and FDA-compliant cloud-based, data-integration platform such as Dexcom Clarity, Medtronic Carelink, or Tidepool.

Information that will be collected from the continuous glucose monitor download will include (but not be limited to):

- Percent of time spent above the glycemic target of 140 mg/dL
- Percent of time spent in the glycemic target of $70-140\,$ mg/dL
- Percent of time spent below the glycemic target of 70 mg/dL
- Percent of time spent in hypoglycemia below 50 mg/dL
- Average blood glucose
- Blood glucose standard variation

Information that will be collected from the insulin pump download will include (but not be limited to):

- Average total daily dose of insulin
- Average bolus amount of insulin per day
- Average basal amount of insulin per day

6.1.3.4 Nutritional tracking smartphone application data collection

Information that will be collected from the smartphone app will include (but not be limited to):

- Total number of calories consumed
- Average grams of carbohydrates consumed per day
- Average grams of fat consumed per day
- Average grams of protein consumed per day
- Additional macronutrient data

Participants will also be asked to photograph all food consumed in the 24 hours prior to the study visit. At the study visit, they will complete a 24 hour dietary recall.

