6.1.3.5 Quality of life survey

Participants will complete the PedsQL, a validated QOL measure in T1DM patients, and Problem Areas in Diabetes-Teen (PAID-T), a validated measure of diabetes-specific distress^{31,32}. They will also

complete the Self-Care Inventory, a validated measure of adherence with diabetes self-care behaviors³⁵. All surveys will be scored by a member of the research team.

Additionally, parents of participants will complete the WHO-5 Well-Being Index, a questionnaire for assessing subjective psychological well-being³⁴, and Problem Areas in Diabetes-Parent Revised version (PAID-PR), a validated measure of perceived parental burden associated with caring for a child with diabetes³³. All surveys will be scored by a member of the research team.

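### Section 10.2 compares each aim by an unadjusted t-test on change and does not list the outcome's baseline as a covariate; adjusting for it would usually, though not always, sharpen the estimate at almost no cost

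*Combined protocol and SAP*

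**What the plan says.** Section 10.2 plans an "independent samples t-test to compare change from baseline to 3 months post-intervention values from each aim", covering HbA1c, LDL-P and the QOL score, with no covariates. It adds regressions on the same change scores, whose explanatory variables "will include mean total daily dose of insulin normalized for body mass, weight change, coefficient of variation of glucose as measured by CGM", and age. Section 2.0 describes the same regression as a "multilinear regression analysis to account for potentially confounding covariates, such as total daily dose of insulin", followed by the other three variables. Neither list names the baseline value of the outcome, and no section specifies a baseline-adjusted comparison.

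The baselines exist:
- **HbA1c.** Section 2.0 says "we will obtain HbA1c at baseline and at 12 weeks after the nutrition intervention".
- **LDL-P.** "The primary outcome measure will be change in total LDL-P from baseline to 12 weeks after the nutrition intervention". The week 0 blood draw (6.1.3.2) covers both HbA1c and the NMR lipoprofile.
- **QOL.** At the week 0 visit (6.1.3.5), "Participants will complete the PedsQL, a validated QOL measure in T1DM patients, and Problem Areas in Diabetes-Teen (PAID-T").

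Section 10.1 gives the first goal of the sample size as being able to "estimate the effect size and variance of the LCD as a means to reduce HbA1c in T1DM in a future definitive trial".

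**The concern.** A t-test on change uses the baseline only by subtracting it, which fixes its slope at 1. An ANCOVA estimates the slope. When the two visits are imperfectly correlated and similarly variable, the best slope is below 1 and the change score carries avoidable noise.

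At stake is the precision of the effect estimate in a small pilot whose purpose is estimation. A second, smaller matter is that the plan does not commit to reporting rho or the baseline-adjusted residual SD, which a team planning the definitive trial would want beside the SD of change.

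**Working it through.** **Inputs from the documents.** Minimum important difference (MID) 0.3%, SD 0.8%, 20 per arm, up to 40% dropout and 4 model degrees of freedom (10.1); 15 per group (2.0, 6.1.1.6). The two sets of group sizes differ, so both are carried through. After 40% dropout, 20 × 0.6 = 12 and 15 × 0.6 = 9.

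**Assumed.** Rho of 0.5, 0.7, 0.8 and 0.9; equal SDs at both visits unless stated; 0.8% read as the SD of change where half-widths are given, because the MID is on change. Section 10.1 does not say so explicitly.

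**The plan's own figures.** 0.3/0.8 = 0.375, which rounds to the stated 0.38, and 2 × 20 = 40. The step from 0.38 to 20 per arm rests on a cited rule that the documents do not reproduce, so it cannot be checked here.

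**Step 1: variance ratio, equal SDs.** With visit SD s, Var(change) = 2s²(1 − rho) and the ANCOVA residual variance is s²(1 − rho²). The ratio is (1 + rho)/2. Estimating the slope with n per group multiplies this by 1 + 1/(2n − 4): 1.071, 1.050, 1.038 and 1.028 for n = 9, 12, 15 and 20. For example, at n = 15 and rho 0.7, 0.85 × 1.038 = 0.88.

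| rho | n = 9 | n = 12 | n = 15 | n = 20 |
|---|---|---|---|---|
| 0.5 | 0.804 | 0.788 | 0.779 | 0.771 |
| 0.7 | 0.911 | 0.892 | 0.883 | 0.874 |
| 0.8 | 0.964 | 0.945 | 0.935 | 0.925 |
| 0.9 | 1.018 | 0.997 | 0.987 | 0.976 |
| Break-even rho, 2/factor − 1 | 0.87 | 0.90 | 0.93 | 0.95 |

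Simulation agrees closely. Its type I error was 0.045 to 0.053 across both analyses at 12, 15 and 20 per group. Allowing for the slightly larger t critical value as well, break-even is 0.85, 0.89, 0.92 and 0.94. These ratios do not depend on the size of the SD.

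**Step 2: unequal SDs.** With L = SD at 12 weeks / SD at baseline, the ratio is L²(1 − rho²)/(1 + L² − 2·rho·L) times the same factor. For L = 1.1, rho 0.8 and n = 15: 1.21 × 0.36/(1 + 1.21 − 1.76) = 0.4356/0.45 = 0.968, and × 1.038 gives 1.005. At n = 15, for rho 0.5/0.7/0.8/0.9:
- L = 0.9: 0.69/0.78/0.82/0.84
- L = 1.1: 0.85/0.96/1.01/1.04

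With L = 1.1 the ratio first reaches 1 at rho of about 0.73, 0.77, 0.79 and 0.81 for n = 9, 12, 15 and 20.

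**Step 3: HbA1c 95% CI half-width, if 0.8% is the SD of change and SDs are equal.** The t-test SE is 0.8 × √(2/n): 0.292 at n = 15 and 0.253 at n = 20. Multiplied by t on 2n − 2 degrees of freedom, the half-widths are 0.60 and 0.51. ANCOVA, using t on 2n − 3 degrees of freedom and the Step 1 ratios, gives 0.53/0.56/0.58/0.60 at n = 15 and 0.45/0.48/0.49/0.51 at n = 20. All exceed 0.3.

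**The case against.** The strongest reply is that nothing here is wrong. The test is unbiased, the half-width exceeds the MID under either analysis (on the reading in Step 3), and no conclusion of the pilot is shown to change. That stands and limits the weight of the point. The size of the gain also rests on inputs the documents do not give: rho, the SD ratio, and the variability of LDL-P and QOL. At 15 per group the assumed cases run from 31% less variance to 4% more.

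A reader might infer more than the documents support, in four ways:

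- **That the planned test is biased or invalid.** It is not. Allocation is at the week −2 visit (6.1.1.6), so the week 0 baseline follows randomization, but both analyses use that same baseline.
- **That the plan excludes baseline.** The lists are introduced by open wording, and the diet-group term is not listed either. Baseline is unlisted, not ruled out.
- **That adjustment wins unless rho is about 0.9 or higher.** This holds only with equal SDs, as Step 2 shows.
- **That section 10.2 makes the definitive trial larger.** With assumed 80% power, two-sided 5% and 0.8% as the SD of change, a trial analysed on change needs 113 per arm, against 85/96/102/108 baseline-adjusted. That saving comes from how the later trial is analysed. The residual SD can be computed from the pilot data whichever test is reported. If 0.8% is instead the single-visit SD, the figures are about 113/68/46/24 against 85/58/42/23, so at rho 0.9 the saving is about one per arm.

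**Conclusion.** The point holds as a recommended improvement in efficiency, not as an error. The plan collects the baseline of every primary outcome and does not commit to adjusting for it. With equal SDs, at the planned group sizes, adjustment removes between about 23% (rho 0.5, 20 per arm) and 1% (rho 0.9, 15 per group) of the variance of the group comparison. The gain disappears at high rho, and sooner if the 12-week values are more variable than the baseline values. The ratios apply to LDL-P and QOL only at their own rho. Sample size, not the choice between these two analyses, remains the main limit on precision.

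**What to change.** In section 10.2, make the main LCD versus SCD comparison for each aim an ANCOVA of the 12-week value on diet group and the baseline value of that outcome, fixed in advance with no data-dependent switch of model. Using change as the dependent variable gives the same group estimate once baseline is in the model, so the MID on change still applies. Keep the unadjusted t-test as a sensitivity analysis. State that rho and the baseline-adjusted residual SD will be reported with the SD of change. Leave the regression with insulin dose, weight change, glucose CV and age as a separate analysis: its four covariates already fill the 4 degrees of freedom that section 10.1 allows, before any group term.

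The cost is SAP wording. No new data are needed. The main model uses two of those 4 degrees of freedom (group and baseline), one more than the t-test. The downside is a negligible gain or a slight loss of precision if rho is high or the 12-week SD exceeds the baseline SD; the largest loss at 15 per group in the cases above is about 4% of variance.

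### Section 10 is written for two arms of 20, but the trial randomises three arms of 15, and no analysis is named for group 3

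*Combined protocol and SAP*

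**What the plan says.** All references are to the combined protocol and SAP.

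- **Design.** Section 2.0 randomises "to one of three groups (n = 15per group"), and section 6.1.1.6 repeats it: "Each group will contain 15 participants". The groups are LCD, SCD and general diabetes education without dietary advice. Blocks are of size 3 (5.3, 6.1.1.6).
- **Purpose of group 3.** Sections 2.0 and 6.1.3.6 both say that the third group lets the trial tell what the macronutrient mix does apart from what being given any diet plan does.
- **Sample size.** Section 10.1: "We have targeted an accrual of 40 participants in this pilot study", and "a sample size of 20 participants per arm will optimize future sample size calculations", "while allowing for up to 40% dropout". The minimum important difference (MID), 0.3 points of HbA1c, is defined for LCD versus SCD only. The SD is 0.8. The section adds that "this sample size allows for up to 4 degrees of freedom in multivariable linear regression analysis".
- **Analysis.** Section 10.2 compares changes in HbA1c, LDL-P and the "QOL score) between the two groups" without naming the two. For the regression, "Explanatory variables in the multivariable linear regression modeling will include mean total daily dose of insulin normalized for body mass", followed by weight change, CGM coefficient of variation and age. No group term is listed. Section 2.0 describes the t-test as between groups, without a number, and the regression as accounting for possible confounders.

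**The concern.** Section 10 reads as the statistical section of a two-arm trial, while the rest of the document describes three arms. Two things follow.

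First, the per-arm size justified in 10.1 is not the size the trial will have. One of the pilot's two stated goals is to estimate the effect and variance for a definitive trial, so the size of the LCD and SCD arms bears directly on what the pilot can deliver.

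Second, group 3 has a stated inferential purpose but no stated analysis. LCD and SCD participants both receive a diet plan, so their difference cannot show the effect of receiving one. Someone following 10.2 as written would report no estimate of it. Someone who wanted one would have to choose, possibly after seeing data, between SCD against group 3, LCD against group 3 and both diets pooled against group 3.

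**Working it through.** **Inputs.** MID 0.3, SD 0.8, 20 per arm, 40 in total, dropout up to 40%, 4 regression degrees of freedom (all 10.1); three groups of 15 (2.0, 6.1.1.6); four covariates (10.2).

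**1. The plan's own figures.** d = 0.3/0.8 = 0.375, printed as 0.38. 2 × 20 = 40, which matches 10.1 exactly. At 40% dropout, 20 × 0.6 = 12 completers per arm. The step from d to 20 per arm rests on a published rule whose steps are not in the documents, so it is taken as given.

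**2. Against the three-arm design.** 3 × 15 = 45 and 3 × 20 = 60, and neither is 40. Spread over three arms, 40/3 = 13.3. Section 10.1 therefore fits two arms only.

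**3. The comparison that 10.1 sizes.** LCD plus SCD is 2 × 15 = 30, not 40. At 40% dropout, 15 × 0.6 = 9 completers per arm, not 12. Keeping 12 of 15 requires dropout of at most 1 − 12/15 = 20%.

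**4. Precision of LCD minus SCD on HbA1c.** 95% half-width = t × 0.8 × √(2/n), with n per arm:

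| Case | n per arm | t (df) | SE | Half-width |
|---|---|---|---|---|
| 10.1, enrolled | 20 | 2.024 (38) | 0.253 | 0.51 |
| Design, enrolled | 15 | 2.048 (28) | 0.292 | 0.60 |
| 10.1, 40% dropout | 12 | 2.074 (22) | 0.327 | 0.68 |
| Design, 40% dropout | 9 | 2.120 (16) | 0.377 | 0.80 |
| Design, variance pooled over three arms, enrolled | 15 | 2.018 (42) | 0.292 | 0.59 |
| Design, variance pooled over three arms, 40% dropout | 9 | 2.064 (24) | 0.377 | 0.78 |

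For the planned two-sample t-test the widening is 0.598/0.512 = 1.17 at enrolment and 0.799/0.677 = 1.18 at the dropout ceiling. With the three-arm variance it is 0.589/0.512 = 1.15 and 0.778/0.677 = 1.15. With equal arms, the last two rows also give the precision of SCD minus group 3 and of LCD minus group 3.

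**5. Group 3.** 15/45 = 33% of those randomised are in the group for which no section names a contrast, a three-group test or a place in a model.

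**6. Regression degrees of freedom.** The four listed covariates use 4 of the 4 allowed. A two-level group term makes 5 and a three-level term 6.

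**The case against.** The strongest reply is that this is a pilot whose three aims all concern LCD versus SCD, and that this comparison is specified. That stands. A reader might infer that the main comparison has no analysis, but the aims and the MID make it clear which two groups 10.2 most naturally means.

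Other replies also limit the point:

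- **Dropout.** The 40% is a ceiling, so 9 completers per arm and a half-width of 0.80 are the worst case. At 20% dropout, 15 per arm still leaves 12. Reading 20 as 12 inflated for dropout (12/0.6 = 20) does not, however, reconcile it with 15, because 15 is the number randomised.
- **Variance.** A reader might infer that the variance estimate suffers as well. With all three arms pooled it has 42 df (24 at the ceiling), against 38 (22) for two arms of 20, so it need not. The loss falls on the contrast.
- **Which number is current.** Nothing in the documents shows that 15 supersedes 20 or the reverse, so one cannot say that the trial is under-enrolled, only that its sections disagree.
- **Group term.** The covariate list in 10.2 need not be exhaustive, and 2.0 implies a group term by speaking of confounders. The overrun of the 4 df arises with any group term, so the third arm is not its cause.
- **Section 2.0.** Its t-test between groups is not limited to two. This softens the omission, but 2.0 names no contrast either, and 10.2 is narrower.

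**Conclusion.** The mismatch is real and should be fixed, though it does not threaten the main comparison. Section 10.1 justifies 40 participants at 20 per arm; the design randomises 45 at 15 per arm. The comparison that was sized loses 10 of its 40 participants, and its interval is about 15% wider with a three-arm variance, or 17 to 18% wider with the t-test as planned. The stated purpose of group 3 has no specified estimate.

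The half-widths assume an SD of 0.8 in every arm, a two-sided 95% level (10.1 states none) and no covariate adjustment. The 40 against 45 conflict and the missing contrast depend on none of these.

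A reader might infer that naming a group 3 contrast would isolate the effect of a diet prescription. The documents do not support that. Groups 1 and 2 track food in an app while group 3 keeps a blood sugar and exercise log (6.1.2, 6.1.5, 6.1.6.4), and the text-message bank is described only for LCD and SCD (6.1.4.2). The contrast carries the self-monitoring difference and possibly the messages too.

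**What to change.** 1. **Reconcile 10.1 with 2.0 and 6.1.1.6.** If three groups of 15 is the design, restate 10.1 as 45 in total and 15 per arm. Give what this leaves (12 completers per arm at 20% dropout, 9 at the 40% ceiling) with the matching precision, and say that it is below the 20 per arm derived there.
2. **Name the contrasts in 10.2.** Make LCD minus SCD primary. State SCD minus group 3 and LCD minus group 3 in advance as secondary and descriptive, each with an estimate and 95% CI. Use a model with a three-level arm term, adjusted only for the baseline value of the outcome and the stratification factors in 5.3 (age and pump type). Leave out weight change, on-study insulin dose and on-study CGM variability: the diets may alter them, and 2.0 makes glycemic variability a secondary outcome, so contrasts adjusted for them are not total effects. Any model containing them should be labelled exploratory.
3. **State what the group 3 contrasts include**, namely the differences in self-monitoring and possibly in messaging.
4. **Restate the df allowance for the model fitted.** With 1 df each for age and pump type, the model in item 2 uses 2 + 1 + 1 + 1 = 5. That is 45/5 = 9.0 participants per df enrolled and 27/5 = 5.4 among completers at the ceiling, against 40/4 = 10.0 and 24/4 = 6.0 under 10.1.

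**Cost.** If 15 per group stands, this is wording in section 10, with no added participants, visits or assays. If 20 per group was meant for all three arms, the total becomes 60, which is 15 more than 45. The downside is imprecision: half-widths of about 0.59 to 0.78 against an MID of 0.3, so the group 3 contrasts can only be descriptive.
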